#### **4.2 Placebo**

Placebo will be 100 mL (for Cohort 1 and 2) and 50 mL (for Cohort 3) normal (0.9%) saline. The placebo will not be matched to the vaccine visually or by taste. Placebo (physiological saline) will be dispensed in an opaque cup. Subjects will be asked not to discuss the taste of the product with other study subjects.

#### **4.3 Study Vaccine Accountability**

PaxVax will supply study vaccine (VAXCHORA or placebo), purified bottled water and opaque cups to all study sites.

It is the responsibility of the Investigator to supervise accurate monitoring of the receipt, storage, dispensing, and accounting of all study material according to accepted medical and pharmaceutical practice. Sites must retain accurate, original site records of study material inventory as well as copies of all invoices of study material shipments and records of study material disposition.

Drug accountability forms will be used for tracking study material (e.g., date material was received, dispensed to individual subjects, amount used and unused on site, etc.).

Each site must keep all unused study material until the Study Monitor either arranges return to PaxVax or their designee or gives instruction for their disposal.

#### **4.4 Study Vaccine Dispensing**

The Unblinded Pharmacist (or designated study staff) will dispense study vaccine to the unblinded Dose Administrator according to each subject's treatment assignment. Subjects should be dosed by the unblinded Dose Administrator at Day 1. In some cases, the functions of the Unblinded Pharmacist and Dose Administrator may be performed by the same person. Each site must keep a Site-Specific Blinding Plan and responsible individuals must sign on the plan.

Unblinded Pharmacist (or designated staff) and unblinded Dose Administrator will not be involved in post-vaccination assessments and evaluation of VAXCHORA acceptability and palatability.

## 5 STUDY PROCEDURES

### 5.1 Informed Consent

Prior to any study-related activities, the subject's parent or legal guardian must sign and date an Institutional Review Board (IRB)-approved Informed Consent Form (ICF). Subjects within the older Cohort 1 ( $\geq 12$  to  $< 18$  y) will provide written assent. Subjects in Cohort 2 may provide written assent per each IRB's recommendation. Refer to [Section 10.3](#) for ICF guidelines.

### 5.2 Screening Procedure

All subjects will undergo screening procedures after at least one parent or legal guardian has given their written, informed consent for their child to participate in the study. Subjects in the oldest age cohort ( $\geq 12$  to  $< 18$  y) will additionally provide their written assent to participate in the study.

The study centers will assign a unique, sequential subject number to each subject who provides written consent. Upon completion of all Screening Visit procedures ([Section 6.1.1](#)) and determination of eligibility, subjects will be scheduled to return for the Day 1 Visit. Screening Visit procedures must be completed no more than 30 days before the Day 1 Visit, but may be performed the same day as the Day 1 visit.

A screening log will be maintained at the clinical research site to record the reason(s) for exclusion from study for all subjects who sign the informed consent and undergo screening.

### 5.3 Re-Screening Procedure

There may be situations in which a subject is not able to be randomized within 30 days of their initially scheduled Day 1 Visit. In these instances, the subject may need to be re-screened. This will involve undergoing all screening procedures again. Subjects may be re-screened one time only.

### 5.4 Randomization Procedure

On Day 1 pre-vaccination, medical history and concomitant medications will be updated in the subject file and negative urine pregnancy test confirmed, if applicable, and blood collected for immune response assessments. The Investigator will confirm and document the eligibility of each subject immediately prior to randomization. Subjects will be considered enrolled once a randomization number has been assigned. Delegated site staff users will enroll each subject by assigning and entering a Subject ID # in the Electronic Data Collection (EDC) system. The EDC user will access the integrated randomization function within the EDC system to randomize the subject to one of the treatment arms. Subjects will be randomized at up to 30 clinical research sites. The assigned treatment will appear only on the randomization schedule that will be delivered to unblinded study personnel before they enroll subject(s) at their site. Blinded study personnel will print the randomization number for each subject from the EDC randomization form and take it to the unblinded personnel, who will match the randomization number to the randomization schedule and dispense the associated treatment.

The study will be conducted as a double-blind study through Day 181, where neither the sponsor, the statistical team, study volunteer subjects, nor clinical site personnel (except for the unblinded staff), will know subjects' treatment assignment. Once each subject has reached their Day 181 visit

they will be individually unblinded. Once all safety and immunogenicity data have been received from the Day 181 visit and the data cleaned, and signed by the PI, preventing further changes, the biostatistics group will carry out the primary analysis. Subjects, clinical site personnel, Investigators and the sponsor will remain blinded until each subject has completed their Day 181 visit. Each subject is unblinded individually at Day 181 and at that time their active/placebo status will be recorded in the EDC. Refer to the current version of PXVX-VC-200-006 Unblinding Plan.

### 5.5 Blinding Safeguards

A number of measures, described below, will be undertaken in order to maintain the blind on this trial. Measures include:

- a) Administration of study vaccine in an opaque container.
- b) The randomization schedule will be loaded in the EDC system at the beginning of the study. Treatment information will be available only to the unblinded site personnel on a per-subject basis upon randomization of each subject or dispensation of treatment.
- c) At each site there will be unblinded personnel who prepare and dispense VAXCHORA and Placebo, and administer the vaccination. All unblinded personnel will agree not to provide any information or documentation to the subjects or blinded staff members that may reveal the treatment assignment. The unblinded personnel will not be involved in any observation, monitoring, or reporting required by the study protocol, other than study vaccine administration, study vaccine accountability and dispensing records.
- d) Subjects will be asked not to discuss the taste of the product with other study subjects as appropriate for age and cognitive level.
- e) Should any subject or blinded staff member become inadvertently unblinded for any reason, the event will be promptly disclosed to the Investigator so that corrective action can be initiated in consultation with PaxVax. The unblinding sequence of events will be documented and retained as source documents. A protocol deviation will be entered in the eCRF.

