After reconstitution, VAXCHORA contains  $4 \times 10^8$  to  $2 \times 10^9$  colony forming units (CFU) of live attenuated *V. cholerae* CVD 103-HgR. The resulting suspension should be slightly cloudy and may contain white particulates. The active and buffer ingredients are shown in Table 2 (VAXCHORA 2016).

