## 3 STUDY PLAN

### 3.1 Study Design

This is a randomized, placebo-controlled, double-blind, single-crossover study with three age cohorts and two treatment groups within each cohort enrolled concurrently (Figure 1).

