## 5.10 Vaccination

Once Day 1 pre-vaccination procedures and randomization are performed, the study vaccine (VAXCHORA or placebo) will be given by oral administration; subjects will receive nothing by mouth (eat or drink) for 60 minutes prior to and after the study vaccine administration .

Subjects will be asked to swallow the study vaccine in isolation of other subjects and in the presence of the designated unblinded study staff member. The subject will then remain in the clinic for at least a 30-minute observation period which the blinded study staff will monitor the subject for any signs of an acute adverse response to the vaccine.

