### 5.11 Acceptability and Palatability Assessments

Study staff will assess the acceptability of the study vaccine based on the subject's ability to take the study vaccine according to the pharmacy manual. Clinically significant findings immediately after consuming the study vaccine will be reported as adverse events. After completion of the 30-minute observation period, palatability will be assessed by the subject or caregiver and reviewed by blinded study staff using a 5-point Hedonic scale. Further details will be provided in the PXVX-VC-200-006 Manual of Procedures.

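### Taste of an unmatched placebo: the rating is reviewed by blinded staff and taste talk is restricted only between subjects, an avoidable risk to the blind of those who assess adverse events

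*Protocol*

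**What the plan says.** Section 4.2 is open about the control: "The placebo will not be matched to the vaccine visually or by taste". Section 1.1.1 says of the reconstituted vaccine: "The resulting suspension should be slightly cloudy and may contain white particulates". Table 2 lists sodium bicarbonate, sodium carbonate, ascorbic acid and lactose in the buffer packet; the placebo is normal saline.

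Two safeguards in 5.5 address the product itself. Item (a) is "Administration of study vaccine in an opaque container". Item (d) is "Subjects will be asked not to discuss the taste of the product with other study subjects as appropriate for age and cognitive level". Section 4.2 has the same request without the age qualifier: "Subjects will be asked not to discuss the taste of the product with other study subjects". Item (c) forbids unblinded personnel to pass revealing information to subjects or blinded staff and removes them from observation, monitoring and reporting. Section 4.4 likewise keeps them out of post-vaccination assessments and of the acceptability and palatability evaluation.

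On the taste rating, 5.11 says that after the 30-minute observation "palatability will be assessed by the subject or caregiver and reviewed by blinded study staff using a 5-point Hedonic scale". In Cohort 3 the caregiver gives the rating (2.4).

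Section 5.13 has study staff go through the memory aid with the subject to confirm the severity of solicited events and their relationship to vaccine. Section 5.4 says that subjects and site personnel, other than the unblinded staff, will not know assignments until Day 181.

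**The concern.** Where two products differ in taste, the opaque cup deals with appearance and leaves taste to be protected by instructions. The protocol's instruction closes one channel, subject to subject. It leaves open subject or caregiver to blinded staff, which is the channel that matters for safety assessment. Caregivers are not mentioned at all. A scheduled procedure then brings the child's or caregiver's opinion of the taste to blinded staff on Day 1, before most of the Day 1 to Day 8 solicited symptoms have been recorded.

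At stake is the vaccine-placebo comparison of adverse events. Five of the eight solicited events (abdominal pain, lack of appetite, tiredness, headache, nausea) are graded in Appendix B mainly by interference with activity, so severity and relatedness leave room for judgement. Relatedness also enters the second stopping rule in 7.10, where one event of Grade 3 or higher judged possibly or probably related suspends enrollment.

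**Working it through.** The protocol states no figure on this point, so there is none to reproduce. The check traces who does what, and then illustrates how much a rating could reveal.

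**Tracing the tasks**

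1. *Acute observation.* Section 5.10 states that "the blinded study staff will monitor the subject for any signs of an acute adverse response to the vaccine" for at least 30 minutes. Under 5.11 the rating comes afterwards, so this observation is not exposed to it.
2. *Palatability.* The subject or caregiver rates and blinded staff review (5.11). Unblinded staff are excluded (4.4).
3. *Later adverse-event work.* Section 5.13 says only study staff. Since 4.4 and 5.5(c) exclude the unblinded personnel, the work falls to blinded staff. The memory aid is collected and reviewed at Day 11 (6.1.3), after the Day 1 rating.
4. *Separation.* No section assigns tasks 2 and 3 to different people, and none withholds the rating from those doing task 3.
5. *Speech.* Sections 4.2 and 5.5(d) restrict subjects with respect to other subjects. Section 5.5(c) restricts unblinded staff. Nothing restricts subjects or caregivers with respect to blinded staff.
6. *Remedy after the event.* Section 5.5(e) requires inadvertent unblinding to be disclosed, corrected and logged as a deviation. It does not prevent it.

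**Numbers exposed**

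Table 3 gives active 150 + 150 + 210 = 510 and placebo 25 + 25 + 35 = 85, in total 595. Each cohort is 6:1 (150/25 = 6; 210/35 = 6).

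**Illustration of what a rating could reveal**

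Let *a* and *p* be the shares who dislike the taste on active and on placebo. The protocol gives neither; the values below are assumptions. With 6:1 allocation:

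- before any rating, P(active) = 6/7 = 85.7%;
- P(active | disliked) = 6a / (6a + p);
- P(active | not disliked) = 6(1 − a) / [6(1 − a) + (1 − p)].

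| Assumed a, p | If disliked | If not disliked |
|---|---|---|
| 30%, 20% | 1.8/2.0 = 90.0% | 4.2/5.0 = 84.0% |
| 60%, 20% | 3.6/3.8 = 94.7% | 2.4/3.2 = 75.0% |
| 80%, 10% | 4.8/4.9 = 98.0% | 1.2/2.1 = 57.1% |
| 20%, 60% (saline disliked more) | 1.2/1.8 = 66.7% | 4.8/5.2 = 92.3% |

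With a small taste difference the rating tells the assessor almost nothing; with a large one it tells a good deal. Spoken remarks about flavour would add to this and cannot be quantified.

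**The case against.** The other side has several good points.

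- *The scale records liking, not flavour, and 5.11 describes no interview.* This stands. The rating is a possible leak and not a disclosure of the arm. A reader might infer that every assessor learns the assignment on Day 1; the text does not support that, and 595 is only the number of children to whom the procedure applies.
- *No section says that one person does both tasks.* This also stands. What the protocol shows is a shared pool with no separation.
- *Operational documents may cover it.* Section 4.4 requires a Site-Specific Blinding Plan, 5.11 refers to a Manual of Procedures and 5.4 to an Unblinding Plan. None is at hand, and any of them may help. But the blinded-staff review is fixed in 5.11 itself and the narrow taste request in 4.2 and 5.5(d), so the wording there still needs attention.
- *Subjects are not stated to be unblinded.* A reader might infer from the unmatched placebo that the protocol concedes there is no subject blind, and that its description in 3.1 ("This is a randomized, placebo-controlled, double-blind, single-crossover study with three age cohorts") is therefore wrong. The documents do not go that far. Section 4.2 says the products are unmatched, not that children know their arm; 5.4 says they will not know; and each child takes one product before Day 181, apart from other subjects (5.10). Relabelling the trial is a preference.
- *The effect is limited.* The primary objectives rest on antibody titers, one of them set against adults from an earlier trial. The safety analysis in 9.4 is descriptive and specifies no table by relatedness. Families record the symptoms and staff confirm them. Fever and diarrhea have numeric grades, and vomiting largely so. A suspension under 7.10 is reviewed by the medical monitor and the Safety Monitoring Committee. All of this confines the point to safety. A reader might also call safety the only randomised comparison; it is not, because 9.5.2 reports titers and seroconversion for placebo recipients too.
- *Blinded review of palatability is deliberate,* since that is itself an endpoint. True, and the fix keeps it free of unblinded staff.

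**Conclusion.** The point holds as an avoidable risk of partial assessor unblinding. The protocol uses a placebo that differs in taste, restricts taste talk only between subjects, and has the rating reviewed within the same blinded pool that later judges severity and relatedness, with no barrier between the tasks.

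The size of the risk cannot be computed from the document. It depends on how differently the products taste, on what children and caregivers say, and on whether sites already divide the tasks. Under the assumed dislike shares, the assessor's probability of active moves from 85.7% to between 84% and 90% in the mildest case, and to between 57% and 98% in the widest.

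The consequence is confined to the descriptive vaccine-placebo safety comparison (510 against 85) and the relatedness calls behind the second stopping rule. The titer-based primary analyses are not affected. The change is worth making because it is cheap; the point does not call the design into question.

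**What to change.** 1. In 4.2 and 5.5(d), extend the request so that subjects and caregivers are also asked not to describe the product's taste or appearance to blinded study staff.
2. In 5.11, replace the blinded-staff review of the rating. The subject or caregiver completes the form, which is then sealed, or entered on an EDC page hidden from staff who assess adverse events, until that child is unblinded at Day 181.

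The description of the trial as double-blind need not change.

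The cost is wording in three sections and, if the EDC route is chosen, an access setting; no added visits or staff. The palatability endpoint is kept. The downside is that adverse-event assessors cannot query a missing or unclear palatability entry on the spot, so a few more may stay incomplete.

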### 5.6 Medical History

Medical history information collected from subjects (or parents or legal guardian) should include (but not be limited to) demographic information, current and past medical conditions, and current medications taken within 30 days of vaccination. The medical history must be documented in the subject's study chart (the on-site source document) prior to study vaccine administration and also recorded on the Medical History electronic case report form (eCRF) and the demographics eCRF. Medications including non-study vaccines must be documented in the source documents as well as on the prior and concomitant medications eCRF and Vaccine History eCRF.

### 5.7 Physical Examination

A complete physical examination will be performed on subjects during screening.

The examination will include:

- Height
- Body Weight
- Head-Neck

Eyes-Ears-Nose-Throat  
Musculoskeletal  
Lymph Nodes  
Lungs-Chest  
Heart  
Abdomen  
Other body system if applicable

All physical exam findings must be documented in the subject's study chart and also recorded on the appropriate eCRF.

## 5.8 Vital Signs

Vital Signs collected from subjects during screening and/or at Day 1 and Day 181 (for Placebo crossover subjects) will include blood pressure, pulse rate, respiration and temperature all of which should be recorded when the subject is calm and ready for vital sign assessment in the opinion of the Investigator. Temperature will be measured orally for Cohort 1 (12 to <18 years) and Cohort 2 (6 to <12 years) and oral is preferred for Cohort 3 (2 to <6 years). For Cohort 3 subjects <4, the axillary temperature may be measured if oral is not feasible.

## 5.9 Pregnancy Testing and Contraception

Female subjects who are of childbearing potential (Cohort 1 and Cohort 2: a female subject is considered of childbearing potential following menarche and until becoming post-menopausal unless permanently sterile) will undergo a urine pregnancy test at screening and prior to each study vaccine administration. This will be done using a urine dipstick. The subject must not receive study vaccine if she has a positive pregnancy test at screening or Day 1, or Day 181 for the Placebo crossover group. Any pregnancies that occur in females who have received a study vaccination must be reported promptly to PaxVax as described in [Section 7.7.1](#).

Female subjects of childbearing potential must also use an acceptable method of contraception from prior to Day 1 through Day 29 and from Day 181 through Day 209 (Placebo crossover subjects). Acceptable methods include highly effective forms of contraception such as combined estrogen and progestogen containing or progestogen-only hormonal contraception associated with inhibition of ovulation, IUD, intrauterine hormone-releasing system, bilateral tubal occlusion, abstinence or vasectomized partner. The Investigator must confirm that contraception methods initiation prior to Day 1 (e.g. hormonal contraception) are considered fully effective prior to vaccination.

## 5.10 Vaccination

Once Day 1 pre-vaccination procedures and randomization are performed, the study vaccine (VAXCHORA or placebo) will be given by oral administration; subjects will receive nothing by mouth (eat or drink) for 60 minutes prior to and after the study vaccine administration .

Subjects will be asked to swallow the study vaccine in isolation of other subjects and in the presence of the designated unblinded study staff member. The subject will then remain in the clinic for at least a 30-minute observation period which the blinded study staff will monitor the subject for any signs of an acute adverse response to the vaccine.

### 5.11 Acceptability and Palatability Assessments

Study staff will assess the acceptability of the study vaccine based on the subject's ability to take the study vaccine according to the pharmacy manual. Clinically significant findings immediately after consuming the study vaccine will be reported as adverse events. After completion of the 30-minute observation period, palatability will be assessed by the subject or caregiver and reviewed by blinded study staff using a 5-point Hedonic scale. Further details will be provided in the PXVX-VC-200-006 Manual of Procedures.

### 5.12 Immune Response Assessments

Blood samples will be collected from all subjects and serum will be tested for vibriocidal antibodies. Table 4 outlines the time points for vibriocidal assessments by subject group.

**Table 4: Blood Sample Collection Time Points**

Subject Group	Serum Vibriocidal Antibodies (SVA) Assessment with Classical Inaba (Study Days)	Blood Collection for Memory B Cell Test (Study Days)
Cohort 1	1, 11, 29(±2), 91(±7), 181(±7)	1, 91(±7), 181(±7)
Cohort 2, 3	1, 11, 29(±2)	NA (Not Applicable)
Sub-study: Long-Term Follow-up visit for Active Treatment group in Cohort 1	365(±14), 547(±14), 730(±14)	365(±14), 547(±14), 730(±14)

Details regarding sample collection, processing and shipping can be found in the PXVX-VC-200-006 Laboratory Manual.

### 5.13 Solicited Adverse Events

Solicited adverse events for this study are: abdominal pain, nausea, vomiting, diarrhea, headache, lack of appetite, tiredness, and fever. From Day 1 through Day 8 (for all subjects) and from Day 181 through Day 188 (for Placebo crossover subjects), these adverse events will be solicited from subjects daily in the evening. Before discharge from the clinic on Day 1, all subjects will be trained to complete a memory aid to observe, measure, and record solicited AEs from Day 1 through Day 8. Study staff will review the signs and symptoms recorded on the memory aid with the subject to confirm severity and relationship to study vaccine, and action taken for the AE. The memory aid will be collected as a source document. Solicited adverse events from Day 1 through Day 8 will be recorded on the solicited adverse event eCRF. Symptoms continuing beyond Day 8 will be recorded on the adverse event eCRF. Actions taken for solicited AEs after Day 8 should be noted in the eCRF. Memory aid re-distribution and retraining to collect solicited adverse events from Day 181 through Day 188 (7 days after vaccination) will be done at Day 181 (vaccination) for Placebo crossover subjects. It will be reviewed by the study staff at the Day 191 (10 days after vaccination) visit.

